COVID-IVIG Protocol Cover Page

Study Title: Randomized Open Label Study of Standard of Care Plus Intravenous Immunoglobulin(IVIG) Compared to Standard of Care Alone in the Treatment of COVID-19 Infection

NCT Number: NCT04411667

Document Date: 19May2020

Protocol name: COVID-IVIG

Principal Investigator: [name]; [contact]; [contact]
IRB # 2004902

Title: Randomized Open Label Study of Standard of Care Plus Intravenous Immunoglobulin (IVIG) Compared to Standard of Care Alone in the Treatment of COVID-19 Infection

Primary Objective:

1. To identify whether or not IVIG can halt the progression to respiratory failure requiring mechanical ventilation in subjects admitted to the hospital with confirmed COVID-19.

Secondary Objectives:

1. To identify whether adding IVIG to the standard of care will reduce days requiring oxygen therapy.
2. To identify whether adding IVIG to the standard of care will reduce total hospital days.

Hypothesis: We hypothesize that the addition of IVIG will be beneficial in abating acute lung injury in subjects with SARSCoV-2 induced hypoxia that results in organ injury in such patients.

Background: Coronaviruses has been known zoonotic pathogens since the early 1970's. Bats have been identified as the main natural reservoir and domesticated animal intermediary species (e.g., camels, cats) have facilitated transmission to humans. In late 2019, a novel coronavirus (SARS-CoV-2) emerged in humans, originating in Wuhan, China and spreading across the globe as a pandemic, causing coronavirus disease of 2019 (COVID-19).

The current mortality rate (17MAR2020) is not well described because of the shortage of laboratory testing assays worldwide. Using WHO data on the cumulative number of deaths to March 1, 2020, mortality rates would be 5.6% (95% CI 5.4–5.8) for China and 15.2% (12.5–17.9) outside of China⁸.

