1. Confirmed COVID-19 positive test result (including presumptive positive).
2. Hospitalization
3. Requiring ≥ 4 liters/min O_2 nasal cannula to maintain oxygen saturation $\geq 92\%$, but not mechanically ventilated
4. Age ≥ 18 years old.
5. Access to a phone in the hospital room or an electronic device that is capable of receiving phone calls and/or video calls and/or e-mail.
6. Able to read/write/speak English or Spanish fluently.
7. Subjects must have the capacity to provide consent or an appropriate Legally Authorized Representative (LAR) to provide informed consent.
8. Negative pregnancy test for women of childbearing potential.

Exclusion Criteria:

1. Severe allergy to any IVIG product formulation
2. History of DVT, PE, thromboembolic stroke or other thrombotic events

3. Hypersensitivity to corn. Octagam® contains maltose which is a sugar derived from corn.
4. Uncontrolled hypertension (SBP>180 mm Hg or DBP>120mmHg)
5. Active participant in another research treatment study
6. Mechanically ventilated patient
7. Code status is Do Not Resuscitate or Do Not Intubate

Age of Subjects: ≥18 years of age

Gender of Subjects: Either male or female

Racial and Ethnic Origin: Non-specific

Vulnerable Subjects: Hospitalized subjects

Study Design: Investigator initiated, open label, multicenter, two arm, randomized study to compare the impact of adding IVIG to the Standard of Care (SOC) to the SOC without IVIG. Randomization ratio will be 1:1.

Procedures and Study Visits:

1. The PI will be notified of a COVID-19 tested positive patient via hospital generated alert.
2. The PI or designee will prescreen the patient using the inclusion and exclusion criteria.
3. PI or Sub-I will contact the study team, if the patient passes prescreening.
4. The CRC will obtain an informed consent from the subject or LAR either electronically utilizing DocuSign® or with a paper copy utilizing an impartial witness:
 - a. The research team will utilize DocuSign® for the signing of the consents in order to be compliant with the infection control measures taken place for Highly Infectious Diseases. Below are the steps of the DocuSign® procedure:

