5. A urine or blood pregnancy test will be ordered using urine or blood previously collected for routine care for subjects of childbearing potential who have passed all the other screening criteria and signed consent. If no leftover urine or blood is available, the patient will be asked to take a urine pregnancy test. If the patient already had a pregnancy test during their hospitalization, the results will be extracted from the EMR and used to determine eligibility.
6. The designated research team member will randomize the subject. The randomization will be computer generated using this website in a block of 10. (<https://www.sealedenvelope.com/simple-randomiser/v1/lists>).
7. If the subject is randomized to the “study arm”, then the Research Pharmacy will enter in the order for the IVIG and will not charge the subject. If the subject is randomized to the SOC arm, there is no additional work to be completed by the Research Pharmacy.
8. There are 3 endpoints for this study: discharge to home, receipt of mechanical ventilation, or death. Once one of these endpoints is reached, the subject’s participation in the study will end. As such, the subject may be a candidate for enrollment in another research protocol where appropriate.

Dose: IVIG (Octagam) 0.5g/kg IVPB actual body weight daily x 3 days, with premedication methylprednisolone 40 mg IV push x 1 30-50 minutes before each IVIG infusion.

- Initial infusion rate of IVIG (Octagam) will be of **0.6 mL/kg/hour**, increasing to a maximum rate of 100ml/hr, if tolerated. This is consistent with the standard of care for IVIG at Sharp HealthCare.

Procedure Classification: Aside from a urine or blood pregnancy test for subjects of childbearing potential, there are no other extra tests, imaging scans or procedures that will be performed as part of the study.

Potential Hazards and Precautions: Potential hazards to subjects are described in the “Potential Risks” section, and precautions for subjects are described in the “Protection Against Risks” section.

Research team members will take precautions to minimize exposure to COVID-19 infection by obtaining informed consent electronically, and by collecting data from routine clinical tests as opposed to conducting protocol-specific tests.

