Study Timeframe: The study time frame would be from IRB approval date to the end of the pandemic or until our sites reach 40 subjects, whatever comes first. We anticipate that at the current COVID-19 rate, it should take about 6 weeks to enroll all patients from the time of study initiation.

The end of study for each individual subject will be the date of discharge from the Sharp HealthCare hospital. The subject will not be followed if there is a transfer to a non-Sharp hospital or any sub-acute care setting (i.e., SNF, LTAC, rehabilitation center). A subject's participation will also end if the subject's goals of care have transitioned to palliation, including changing the code status to Do Not Resuscitate or Do Not Intubate of which would render the patient no longer a candidate for intubation.

Method of Subject Identification and Recruitment: The PI or Sub-I will be notified of a COVID-19 confirmed positive patient via hospital generated alert as part of the Infectious Disease Team at each hospital.

Subject Capacity: Subjects who are cognitively impaired or lack the capacity to provide informed consent (as described in HRP-013 section 5.2) may be enrolled in the study if they have an appropriate LAR to provide written informed consent on their behalf. The researchers will follow the guidance outlined in HRP-013 "Legally Authorized Representatives (Surrogate Consent)" when obtaining surrogate consent.

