Data Collection/ Assessment Instruments: The Case Report Form will include the following data elements: Demographics (age, gender, race/ethnicity, insurance), medical status (pre-existing comorbid conditions (based on the Charlson Comorbidity Index), ferritin level (results will only be collected if lab is ordered as part of the subject's standard of care), CRP level. The tool used to calculate the Charlson Comorbidity Index can be found here <https://www.mdcalc.com/charlson-comorbidity-index-cci#next-steps>). Other data to be collected from standard of care procedures includes vital signs, result of blood or urine pregnancy test, serum creatinine, calculated creatinine clearance (Cockcroft and Gault equation), white blood cell count, platelet count, maximum body temperature in the past 24 hours and oxygen demand rate, whether or not there is an admission to the ICU, any concomitant antimicrobials including azithromycin, doxycycline, hydroxychloroquine, chloroquine, and remdesivir. Receipt of interventions will include standard of care in those who have tested positive for COVID-19. Measures of healthcare service utilization will include length of stay, number of days in ICU, number of days requiring oxygenation, discharge disposition and mortality.

Data Collection Resources: The Study Coordinator will complete the Case Report Forms, with assistance from Sharp's Clinical Analytics team to extract information from the EMR.

Data Analysis: Descriptive statistics will be conducted to describe frequencies of demographics and clinical characteristics including the following: age at discharge, gender, race/ethnicity, payer, comorbid conditions based on the Charlson Comorbidity Index, receipt of medical interventions (mechanical ventilation, medications) and healthcare service utilization (ICU admission and Length of Stay in the hospital). Frequencies and descriptive statistics will be conducted using chi-square or 2-tailed Fisher exact statistics depending on the final sample size for categorical data and t-tests for continuous data. Kaplan-Meier analysis will be performed with assistance from a biostatistician regarding the endpoints of mechanical ventilation and discharge to home endpoints. We do not anticipate number of patient deaths for be sufficient for a meaningful analysis.

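### The plan does not say how palliation, a DNR/DNI change or death before ventilation is scored; if higher-risk patients exit unequally, the arm with more exits looks better on ventilation

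*Combined protocol and SAP*

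**What the plan says.** The Primary Objective is "To identify whether or not IVIG can halt the progression to respiratory failure requiring mechanical ventilation". Procedures and Study Visits (item 8) states "There are 3 endpoints for this study: discharge to home, receipt of mechanical ventilation, or death", and the first of these to occur ends participation. They are listed separately and are not combined into a composite.

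Study Timeframe adds a further exit: participation ends if the subject's "goals of care have transitioned to palliation, including changing the code status to Do Not Resuscitate or Do Not Intubate". Termination of the Study repeats it. Both places give the reason that such a patient would not be intubated. The Exclusion Criteria bar entry if "Code status is Do Not Resuscitate or Do Not Intubate", so every such change happens after randomisation. Study Design describes an "Investigator initiated, open label, multicenter, two arm, randomized study".

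Data Analysis plans "chi-square or 2-tailed Fisher exact statistics depending on the final sample size for categorical data", and Kaplan-Meier for ventilation and for discharge home with a biostatistician's help. It expects too few deaths to analyse. It gives no scoring rule, composite, censoring rule or competing-event method for death or a code-status change before ventilation. Mortality and discharge disposition are on the case report form.

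Follow-up after the change is unclear. Study Timeframe ends participation there, yet also says "The end of study for each individual subject will be the date of discharge from the Sharp HealthCare hospital". Termination of the Study continues data collection to discharge, but for early stopping of study treatment.

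**The concern.** By the protocol's own reasoning, a change to palliation or DNR/DNI rules out the primary event, and so does death. Both are competing events, not ordinary loss to follow-up. With no rule, an analyst would most naturally count these patients as not ventilated in the Fisher table and censor them in Kaplan-Meier.

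Counted as non-events, patients who would have been ventilated are scored with those who recovered. Censored, they are treated as having the same future risk as those still under observation. If they were in fact at higher risk, either choice understates respiratory failure in their arm. Entry requires at least 4 L/min of oxygen, so a link between exit and worsening is plausible. The trial is open label, so goals-of-care decisions can be made with the arm known, and equal exits cannot be assumed. What is at stake is the direction of the primary comparison and, even with equal exits, its power.

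**Working it through.** **Inputs from the documents.** 40 subjects (Study Timeframe), allocated 1:1 (Study Design), 20 per arm at full enrolment (Data Monitoring); two-tailed Fisher test (Data Analysis). The available text gives no event rate, effect size or power behind the 40, so there is no plan figure to reproduce.

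**Assumptions.** Significance at two-sided p < 0.05 (no alpha is stated). No true effect: a share f = 30%, 40% or 50% of each arm is heading for ventilation. A share e of those patients exits first, and nobody else exits. This last assumption is the unfavourable case. IVIG is given the larger share for illustration; swapping the arms gives the same figures for false harm.

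**Step 1: Fisher, exits as non-events.** Observed ventilation = f × (1 − e). All 21 × 21 tables were enumerated exactly.

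| Exit share, SOC v IVIG | f | Observed SOC v IVIG | Bias (points) | False benefit | Total false significance |
|---|---|---|---|---|---|
| none | 30 / 40 / 50% | equal | 0 | 1.2 / 1.2 / 1.0% | 2.5 / 2.4 / 2.0% |
| 10% v 30% | 30% | 27% v 21% | 6 | 3.3% | 3.7% |
| 10% v 30% | 40% | 36% v 28% | 8 | 4.4% | 4.7% |
| 10% v 30% | 50% | 45% v 35% | 10 | 5.2% | 5.4% |
| 10% v 20%, or 5% v 15% | 30-50% | e.g. 36% v 32% | 3-5 | 2.0-2.5% | 2.7-3.0% |

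The 10% v 30% case means 20 × f × e = 0.6-1.0 v 1.8-3.0 expected exits per arm.

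**Step 2: exits excluded.** Observed ventilation = f(1 − e) / (1 − fe): 27.8% v 23.1%, 37.5% v 31.8%, 47.4% v 41.2%. The bias is 4.8, 5.7 and 6.2 points, which is smaller but in the same direction.

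**Step 3: exits censored.** The plan names Kaplan-Meier but no test. With an assumed log-rank test and assumed exponential times, simulation of the 10% v 30% case gives false benefit of 5.5 / 6.2 / 7.1% (2.6% without exits) and total false significance of 6.6 / 7.1 / 7.9% (5.2-5.3% without exits).

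**Step 4: equal exits of 25%.** False benefit stays at 1.1-1.2%. A true 50% v 25% reads 50 × 0.75 = 37.5% v 25 × 0.75 = 18.75%, and Fisher power falls from 26.9% to 17.3%.

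**Step 5: fixed tables.** One patient recoded as a non-event matters only at the border: 10/20 v 3/20 (p = 0.041) becomes 9/20 v 3/20 (p = 0.082). If that patient is excluded, 9/19 v 3/20 stays at p = 0.041. Starting from 8/20 v 8/20, two exits in one arm give p = 0.74; seven are needed for significance (8/20 v 1/20, p = 0.020).

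**Step 6: limits of the remedies.** In the 10% v 30% case, if half of those who exit leave hospital alive, ventilation-or-death = f(1 − e/2): 28.5% v 25.5%, 38% v 34%, 47.5% v 42.5%. That leaves 3-5 points of bias (false benefit 2.0-2.4%). Counting the code-status change as failure removes this, but only because nobody else is assumed to exit. If 5% v 15% of patients who would not have been ventilated also change code status, it creates a bias of (1 − f) × 10 = 7 / 6 / 5 points the other way (false harm 2.4-3.7%).

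**The case against.** Much is already in place. Death is a named endpoint, mortality and disposition are collected, and ventilation and death could be tabulated by arm. Few deaths are expected. Excluding DNR/DNI at entry should limit later changes. This stands, and it is why the point is strongest for DNR/DNI, which has no endpoint status. It does not settle how either exit enters the ventilation comparison.

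The direction is conditional. Exits unrelated to ventilation risk would not bias Kaplan-Meier, and the documents do not show the link. This stands too. The main scenario is also favourable to the concern, with a threefold imbalance and exits confined to patients heading for ventilation. The milder rows in the table are a fair counterweight.

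A reader might infer more than the text supports:

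- *That the trial is tilted towards IVIG.* Nothing shows which arm will have more exits.
- *That false positives rise sharply.* In these Fisher scenarios the total reaches at most 5.4%; only the assumed log-rank test is clearly above 5%, and the plan does not name one.
- *That data collection certainly stops at the code-status change.* The passages conflict.
- *That ventilation is the wrong primary question.* Potential Benefits (Value) to Society makes ventilator demand an explicit aim, so moving to a composite is a choice of estimand, not the correction of an error.

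**Conclusion.** The gap is real. The primary comparison has no rule for events that preclude its outcome and that arise after randomisation in an open-label trial. This is more than missing detail, because following the stated stopping and analysis rules gives an exit that may depend on prognosis.

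The size is modest and uncertain: 3-10 points of bias over the unequal-exit scenarios examined, felt mainly as a shift towards the arm with more exits. It rests on assumed failure rates, assumed exit shares and an assumed alpha, on exits being concentrated in higher-risk patients, and on unequal exits. With equal exits the cost is power alone.

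The text available for review lacks a part between the Background and the inclusion criteria, but the Data Analysis section is present and silent on the point. Low end of should-fix, medium confidence.

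**What to change.** Keep all randomised patients in the analysis, and add wording such as: *After a change to palliation or DNR/DNI, the date of the change is recorded, and ventilation and vital status continue to be read from the EMR until discharge or transfer from the Sharp hospital.* Then specify:

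1. **Ventilation remains the stated question**, analysed by cumulative incidence with death and code-status change as competing events, in place of Kaplan-Meier censoring. This describes actual ventilator use but does not by itself undo unequal exits.
2. **In-hospital ventilation or death**, pre-specified beside it and read with it before any benefit is claimed. Whether it becomes the main comparison is the sponsor's choice.
3. **A sensitivity analysis counting the code-status change as failure.** It should not lead, because the change is itself a decision made with the arm known.
4. **Number and timing of exits by arm.**

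**Cost.** One date field and slightly more in-hospital EMR review; the EMR is already the data source, and no contact after discharge is needed. Check that the consent covers reading the record after the change.

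**Downsides.** The composite mixes two events, can include non-respiratory deaths, and misses patients who leave alive. The sensitivity analysis can bias the other way, by about 5-7 points in step 6. Transfers remain unobserved, since "The subject will not be followed if there is a transfer to a non-Sharp hospital". No change to clinical management is implied.

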Privacy of Subjects: There will be limited access to the subject due to standard of care isolation protocols. The Informed Consent process will emphasize the personal nature and privacy

concerns related to communications regarding the subject's condition and infectious disease test results.

Confidentiality of Data and Storage: Subjects information will be recorded on a master list accessible to the investigator and research staff. It will be stored electronically on a secure server. Information included on master list: subject ID, hospital, date screened, patient name/room#, FIN, group, age, gender, enrollment status, telephone number, email address, and address. All binders will be stored and secured at Sharp's Center for Research office in accordance with all regulatory and organizational requirements, and will be accessed only by authorized personnel. No subject-specific data will be reported. Sharp FIN will be used to link subject records across data systems and hospital visits. Protected Health Information (PHI) will be safeguarded as specified by Sharp HealthCare policy. There is a risk of disclosure of PHI from inappropriate access to the study database. All efforts will be made to protect PHI, including password protecting the database with access only allowed to study members who are Sharp HealthCare employees. All datasets will be de-identified prior to any statistical analyses conducted by the Statistician. Identifiers will be destroyed two years after study end date, once data has been aggregated for reporting.

Data Monitoring: A designated person (or group of designees) who is not part of the Research Team will review and will report the outcomes to the SHC IRB after a total of 10, 20, and 40 patients (5, 10, and 20 in each arm, respectively) have completed/met the endpoint of the study. Additionally, if unexpected adverse outcomes are identified at any point in the enrollment the designated person will review the case on an individual basis.

Benefits to Individual Subjects: Potential reduction in ICU hospitalization, potential avoidance of mechanical ventilation and potential decrease in length of stay in the hospital.

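### Oxygen days, the first secondary outcome, have no counting rule and are recorded by a coordinator who can see the arm; a fixed EMR query run without the arm would remove that discretion cheaply.

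*Combined protocol and SAP*

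**What the plan says.** Study Design describes an "Investigator initiated, open label, multicenter, two arm, randomized study", and adds "Randomization ratio will be 1:1". Data Collection Resources assigns the forms: "The Study Coordinator will complete the Case Report Forms, with assistance from" the health system's "Clinical Analytics team to extract information from the EMR". It does not say which fields the analytics team extracts or how the work is divided.

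Confidentiality of Data and Storage states: "Subjects information will be recorded on a master list accessible to the investigator and research staff". The listed contents include a field called 'group', which is not defined but most naturally means the arm. The same section says "All datasets will be de-identified prior to any statistical analyses conducted by the Statistician".

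Data Sources names the EMR as the only source. Under Procedures and Study Visits, the Research Pharmacy enters an IVIG order for patients in the study arm only.

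Reducing days on oxygen is Secondary Objective 1. Data Collection/Assessment Instruments lists oxygen days and ICU days among the utilization measures and gives no counting rule for either. Data Analysis plans t-tests for continuous data.

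**The concern.** Three features meet in one outcome. The person who records it can know the arm, the definition leaves room for judgement, and nothing in the plan separates recording from allocation. A coordinator reading a chart must decide whether to count a day with a few hours of oxygen, a day with a trial on room air, or a day when oxygen was left on at minimal flow. The plan settles none of these. If borderline days are read even slightly more favourably in the IVIG arm, the difference in means moves toward IVIG with no treatment effect behind it, and no check in the plan would show it.

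De-identification does not help here. It is a privacy step that removes identity, not allocation.

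**Working it through.** **Is the arm visible to the recorder?** Treatment is open label. Research staff can open the master list, which carries 'group'. The IVIG order can be expected to appear in the EMR from which the outcomes are taken. No masked abstraction or adjudication is described anywhere. So the arm is visible by more than one route.

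**Which outcomes leave discretion at data entry?**

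- Start of mechanical ventilation, discharge and death are discrete, dated events, so little is left to judge.
- ICU days normally follow from recorded transfer times. They are a utilization measure and not an objective.
- Oxygen days depend on a rule that the plan does not give. This is the exposed outcome.

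**How much could a recording shift matter?** The plan states no SD, significance level or effect size, so it has no figure of its own to reproduce.

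Inputs from the documents:

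- Enrolment runs "until our sites reach 40 subjects, whatever comes first" (Study Timeframe).
- Data Monitoring reviews outcomes "after a total of 10, 20, and 40 patients (5, 10, and 20 in each arm, respectively", so n = 20 per arm.
- The test is a t-test (Data Analysis).

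Assumptions:

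- The level is 5%, two-sided.
- The SD of oxygen days is 4 to 10 days.
- The true effect is zero.
- Recording moves one arm's mean by b days.

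The t statistic then has 20 + 20 − 2 = 38 degrees of freedom and noncentrality b / (SD × √(2/20)). For b = 1 and SD = 6 this is 1 / (6 × 0.3162) = 0.527. The chance of rejection in either direction is:

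| Shift b | SD 4 | SD 6 | SD 8 | SD 10 |
|---|---|---|---|---|
| 0 | 5.0% | 5.0% | 5.0% | 5.0% |
| 0.5 day | 6.7% | 5.8% | 5.4% | 5.3% |
| 1 day | 12.0% | 8.1% | 6.7% | 6.1% |
| 2 days | 33.8% | 17.7% | 12.0% | 9.5% |

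**What would such a shift require?** A mean shift of 0.5 day is, for example, one whole day moved in the same direction for 10 of 20 patients in an arm (10/20). A shift of 1 day would need this for all 20. For scale, the difference detectable with 80% power is about (1.960 + 0.842) × SD × √(2/20) = 0.886 × SD. That is about 3.5 days at SD 4 and 8.9 days at SD 10. Half a day is small against that. One to two days could matter if the SD is at the low end.

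**The case against.** The strongest reply is that the risk is hypothetical and the effect modest. SD, level and shift are all assumed, and no passage suggests discretion large enough to move a mean by a day. The coordinator may already be transcribing the analytics team's output, which would leave less to judge. All of this stands, and it limits the point to a cheap improvement.

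A second reply is that masked extraction cannot be complete. Anyone who checks chart notes can see the IVIG order, and it is an inference that the analytics team could derive oxygen days without the arm: the documents do not say whether oxygen device and flow are held in queryable fields. This also stands. It bears on how the fix is written, not on whether a rule is needed.

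A reader might go further and infer that de-identified data should also be coded A/B for the statistician. That is optional and fragile here. Data Analysis describes medications received, and the Dose section gives IVIG with methylprednisolone premedication to one arm only. If those data are in the analysis file, the labels decode themselves.

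The reply does not remove the core point. An outcome tied to a stated objective has no counting rule and is recorded by someone who can see the arm.

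**Conclusion.** The point holds for oxygen days. The plan leaves avoidable, arm-aware discretion in recording Secondary Objective 1. The documents establish the opportunity for bias, not its presence, direction or size. The calculated rates are illustration only: within the assumed SD range, a half-day shift does little, and a one-day shift more than doubles the nominal 5% only at the smallest SD.

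Two stronger readings are tempting and not supported. One is that the primary endpoint and ICU days are compromised at data entry; they rest on recorded events or transfer times. The other is that masked extraction would cure the open-label problem. Clinicians who know the arm decide on oxygen, ICU transfer and discharge, and those decisions are in the EMR before anyone abstracts it. Only the recording component can be removed.

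**What to change.** 1. Write into the plan, before any outcome data are extracted, what counts as an oxygen day. Cover partial days, trials on room air and the minimum recorded support.
2. Have the Clinical Analytics team derive oxygen days for all randomised patients by one fixed EMR query. Run it on a list of FINs supplied without 'group', and leave the IVIG order out of the query.
3. Freeze the derived variable, then merge the arm.
4. Make any correction from chart notes under the same written rule and log it, because the notes can reveal the arm.
5. State as a limitation that bias from unblinded bedside decisions remains.

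The cost is one written definition, one query and a change in the order of merging, using a team already named and with no new staff or tests. The downside is that structured oxygen fields may be incomplete, so some logged corrections from notes may be needed.

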Grave concerns are raised about the ability of the US healthcare system to handle the demand of subjects affected by the COVID-19 pandemic. While 80-85% of identified COVID-19 patients are asymptomatic or have mild disease, the 15-20% of patients requiring medical support (of which 1/3-1/2 are estimated to require ICU care) would pose dire consequences of healthcare access with current resources. Therefore, while the spread of virus continues to escalate, the ability to abort subjects away from the path of acute lung injury requiring mechanical ventilation would render an extreme advantage to healthcare systems. The average time from hypoxia to mechanical ventilation is nine days, and once patients become ventilated, they frequently require support for 2 weeks.

[figure not shown]
[figure not shown]
It is of interest that the natural history of COVID-19 frequently exhibits a biphasic illness seen with other acute viral and atypical infection. The first part of the illness is driven by direct viral

[figure not shown]
replication in permissive host tissues, which for COVID-19 is largely the respiratory tract. The host immune response to the primary infection results in a second phase, more catastrophic than the first, driven by immune system hyperactivity, often referred to as a ‘cytokine storm.’ Therefore, the successful treatment of more severe infection will likely rely more on immunomodulation rather than on antiviral therapy.¹ IVIG is an immunomodulatory agent used to treat the immunological complications of many infections, including immune-mediated encephalitis and Guillan-Barre.²

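### The t-test on hospital and oxygen days has no rule for death, so an early death counts as a short stay; likely skew may also cost some power (minor)

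*Combined protocol and SAP*

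**What the plan says.** The two secondary objectives are to find out whether IVIG will "reduce days requiring oxygen therapy" and "reduce total hospital days". The Data Analysis section compares categorical data by chi-square or Fisher's exact test and uses "t-tests for continuous data". Length of stay is listed in that paragraph. Oxygen days are collected (Data Collection/Assessment Instruments) but not named in the analysis, so only the general rule reaches them. No rank test, transformation or distribution check is planned. A Kaplan-Meier analysis is planned for ventilation and for discharge home, with no between-arm test named. The section expects too few deaths for a meaningful analysis and does not say what day count a patient who dies receives.

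Enrolment runs "until our sites reach 40 subjects" or the pandemic ends (Study Timeframe). "Randomization ratio will be 1:1" (Study Design), and Data Monitoring gives "5, 10, and 20 in each arm, respectively" for its three reviews.

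Two places define the end of follow-up differently. Procedures and Study Visits, item 8, ends participation at discharge home, mechanical ventilation or death. Study Timeframe ends it at discharge from the hospital system, and also at transfer out or a change to palliative goals.

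**The concern.** A raw day count has no place for death. A patient who dies on day 4 contributes four hospital days and at most four oxygen days, which on this scale is a good result. If IVIG keeps such patients alive, they stay longer, and the comparison moves against IVIG.

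The shape of the counts is a second, weaker issue. The Background says that "once patients become ventilated, they frequently require support for 2 weeks". If the whole stay is counted, a mix of quick discharges and stays about two weeks longer gives a right tail, and with 20 per arm a few long stays can drive the mean and its standard error. At stake is the reading of both secondary objectives, not the primary one.

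**Working it through.** The documents give no mean, SD, distribution, effect, alpha or power for either outcome, so there is no planned figure to reproduce. From the plan: 20 per arm, the t-test, the two-week ventilation figure, and mortality of 5.6% and 15.2% (Background). Everything else is assumed, including two-sided 0.05.

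**1. Effect of death on mean days.** Let survivors average *m* days and patients who die average *d* days, the same in both arms, with death proportions p_C (control) and p_I (IVIG). Then

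mean(IVIG) − mean(control) = (p_C − p_I)(m − d).

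Take m = 12.5, d = 5.5, p_C = 0.30, p_I = 0.10:
- control: 0.30 × 5.5 + 0.70 × 12.5 = 10.4 days
- IVIG: 0.10 × 5.5 + 0.90 × 12.5 = 11.8 days
- difference: 0.20 × 7.0 = 1.4 days longer on the arm with fewer deaths.

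If the Background's two mortality figures are used only as a scale for the two arms (15.2% v 5.6%), the shift is 0.096 × 7.0 = 0.67 days. Expected deaths per arm would be 20 × 0.152 = 3.0 and 20 × 0.056 = 1.1.

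**2. Power with deaths present.** Simulated, 20 per arm: ventilation 40% v 20%, about 14 extra days after ventilation, log-SD 0.5, half of ventilated patients dying on days 2 to 8.

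| Other stays on IVIG | t-test | Rank test, raw days | Rank test, deaths worst |
|---|---|---|---|
| equal | 6% | 5% | 18% |
| 20% shorter | 19% | 19% | 42% |
| 30% shorter | 32% | 36% | 58% |

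A rank test on raw days gains little or nothing over the t-test here. Ranking deaths worst makes the difference. Part of that gain is the survival effect itself (deaths 20% v 10%), which the ranked outcome now includes.

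**3. Power without deaths, by assumed shape.** 10,000 simulated trials per setting, 20 per arm, whole days. Each cell is power for t-test / Mann-Whitney at the given ratio of days. The log-normal control median is 9 days and the gamma control mean 12 days.

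| Shape | Ratio 0.75 | Ratio 0.6 | Ratio 0.5 |
|---|---|---|---|
| log-normal, log-SD 0.7 | 20.3 / 22.9% | 51.8 / 57.9% | 78.3 / 84.4% |
| log-normal, log-SD 0.9 | 12.7 / 15.7% | 31.4 / 39.2% | 50.6 / 63.5% |
| log-normal, log-SD 1.1 | 8.5 / 12.3% | 18.9 / 28.1% | 32.2 / 46.4% |
| gamma, skew 1.0 | not run | 87.7 / 83.9% | 98.6 / 97.7% |
| gamma, skew 1.4 | not run | 59.7 / 53.8% | 83.2 / 77.5% |
| gamma, skew 2.0 | not run | 31.5 / 27.0% | 52.4 / 44.2% |

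The t-test loses 22.9 − 20.3 = 2.6 to 46.4 − 32.2 = 14.2 points in the log-normal rows and gains 98.6 − 97.7 = 0.9 to 52.4 − 44.2 = 8.2 in the gamma rows. At log-SD 0.3 and 0.5 the difference is between −0.6 and +2.4 points. With no effect, the t-test rejects in 3.4% to 5.0% of trials across all shapes.

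**4. Cutting the count at ventilation.** Assume ventilation 40% v 15%, on day 1 to 6 (mean 3.5); other stays log-normal with median 9 and log-SD 0.7, so mean 9 × exp(0.7²/2) = 11.5; and no effect on those stays.
- Cut at ventilation: control 0.40 × 3.5 + 0.60 × 11.5 = 8.3; IVIG 0.15 × 3.5 + 0.85 × 11.5 = 10.3 days.
- Whole stay, with 14 days added (3.5 + 14 = 17.5): control 0.40 × 17.5 + 0.60 × 11.5 = 13.9; IVIG 0.15 × 17.5 + 0.85 × 11.5 = 12.4 days.

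The cut reverses the direction. If other stays are also 25% shorter on IVIG, power is 4.4% (t) and 4.6% (rank) with the cut, against 41% and 45% for the whole stay. With ventilation on day 4 to 14 it is 14% and 19% against 48% and 49%.

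**The case against.** The strongest reply is that this is a preference on secondary outcomes. The t-test holds its level. Its power loss depends on the assumed shape and reverses for gamma days. The largest losses need a halved stay; at a ratio of 0.75 they are 2.6 to 3.8 points, with both tests badly underpowered. In a ventilation mixture without deaths, the setting nearest to the Background, one set of runs gave 35% v 38% and 17% v 15%. Kaplan-Meier for discharge home needs no normality, and the protocol expects few deaths.

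Most of this stands, and it limits the skewness argument to a possible loss. A reader might infer that both outcomes are strongly skewed and that the t-test therefore costs power on both secondary objectives. The documents do not support that: they give no distribution, they name no test for oxygen days beyond the general rule, and they have a second analysis bearing on hospital stay.

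The point about death survives. The Kaplan-Meier plan names no between-arm test, does not say how deaths enter, and does not cover oxygen days. Few deaths can still matter with 20 per arm, as step 1 shows. It is also fair to object that the end of follow-up matters more than the choice of test. A rank test on counts cut at ventilation repairs nothing, so that conflict must be settled first.

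**Conclusion.** The point holds as a minor one. The prescribed test has no rule for death, so a survival benefit can appear as a longer stay: 1.4 days with deaths of 30% v 10% and a seven-day gap between survivors' stays and times to death, 0.67 days with 15.2% v 5.6%. In the settings tried with other stays 20% or 30% shorter, ranking deaths worst raised power from 19% to 42% and from 32% to 58% against the t-test. That advantage depends on deaths differing between arms and should not be expected if IVIG leaves mortality unchanged.

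Right skew is likely but assumed, and whether a rank test gains or loses power depends on the shape. Validity is not in question, and the primary objective is unaffected.

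**What to change.** 1. Reconcile Procedures and Study Visits, item 8, with Study Timeframe, so that both day counts run to hospital discharge and are not cut at ventilation. In-hospital deaths must be recorded for every randomised patient, including after ventilation or a change to palliative goals. State a rule for patients transferred out. Item 8 also lets a ventilated patient enter another study, so the text should say that the counts are still read from the medical record.
2. In Data Analysis, for both secondary outcomes, replace the t-test with a Wilcoxon rank-sum test in which in-hospital deaths share the worst rank.
3. Report medians by arm, a Hodges-Lehmann difference with 95% interval among survivors, and mean differences as descriptive only.

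The cost is a few sentences, and the data come from records already used. The downside is small: the test compares ranks rather than mean days and combines death with duration. The survivors-only difference is not a comparison of the groups as randomised, so deaths by arm should be shown beside it.
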